9. PATIENT COHORTS

A comprehensive and longitudinal research cohort will be established. A broad collection of fine-granular clinical and epidemiological data connected to collection of biological samples will help answer the most relevant questions in the context of the SARS-CoV-2 pandemic. By implementing an international cohort of SARS-CoV-2 infected patients, considering all age groups, with any comorbidity and socioeconomic background as well as any stage of disease severity and setting (in- and outpatients), answers regarding the epidemiology and optimal management of SARS-CoV-2 will be provided at local, regional, national and international level. Besides the comprehensive gathering of data and biological samples, representative sub-cohorts such as patients with specific comorbidities, adolescents or children can be analysed. Long-term follow-up data will further support both insight into pathophysiological mechanisms as well as improve individualized patient management. The information provided will help in adapting hospital management and public health strategies and thereby in reducing further socioeconomic damage. In long term perspective, the nation-wide collaboration of several stakeholders, the use and extension of existing and newly established infrastructures might serve as a fast response for coming global and national health challenges. The constitution of a "perpetual" cohort including not only population-based representatives but also substantial number of HCWs (high risk population in case of endemic event with high incidence of admission for infected individuals and therefore high risk of hospital spreading) and fragile population including pregnant women, children, elderly, immunocompromised subjects (transplant recipients, patients with onco-haematological malignancies or HIV-infection) and individual with neurological impairment enables to precisely define the target of vaccination trials based

on severity of diseases in those population but also on the burden of diseases (in terms of delayed care as visits, chemotherapy or radiological assessment) in populations in need of periodic clinical evaluations. COVID-19 fragile population cohorts will be assessed in collaboration with ORCHESTRA – Work Package 4, focusing on the prevalence, clinical spectrum and therapeutic management of COVID-19 disease in established cohorts of fragile patients. Specific features of fragile populations to follow-up is reported in table 1.

Patients will be recruited within European and non-European cohorts participating to ORCHESTRA consortium. Data will be extracted according to the study protocol and the case report form in compliance with local regulatory rules.

A description of the cohorts is presented in the following sections.

9.1. University of Verona (UNIVR) – Italy

UNIVR will participate to the recruitment of COVID-19 general population and COVID-19 fragile populations: HIV positive, solid organ transplanted, oncological (both solid cancer and haematological neoplasms) patients and elderly people resident in LTCFs (General nursing home; residential home; specialized LTCFs; mixed LTCFs, other LTCFs; overall number of beds; ownership of the facility: public, for profit, not for profit). Estimated number of COVID-19 patients since the beginning of the pandemic: 66000

9.2. The French Covid-19 cohort

INSERM - Institut National de la Santé et de la Recherche Médicale

National French cohort which follows more than 3000 hospitalized patients across France The objectives of this cohort are to describe: 1) clinical features of illness; 2) treatment used and their outcome; 3) virus replication, excretion and evolution in multiple sites; 4) host responses including innate and acquired immune responses; 5) host genetic variants associated with disease progression/severity.

9.3. Lean European Open Survey on SARS-CoV-2 Infected Patients (LEOSS)

University Hospital of Cologne (UHC), Cologne- Germany

International cohort of more than 2,500 SARS-CoV-2 infected patients from 250 study sites all over the world, implemented by the University Hospital of Cologne (UHC), Cologne-Germany since March 2020.

9.4. COVID-HOME study

University Medical Center Groningen (UMCG), Groningen, Netherlands

Prospective cohort study of non-hospitalised COVID-19 patients. The COVID-HOME study focuses on the community and household with early, systematic and prospective long-term follow-up The parameters collected in this study, such as viral load, antibody response, cyto-kine changes and clinical and laboratory parameters of patient evolution will allow the identification of independent factors/parameters determining evolution of disease, insight in other transmission routes than respiratory ones (such as sexual and faecal-oral), and immune response dynamics in non-hospitalised patients.

9.5. Fondation Congolaise pour la Recherche Médicale (FCRM) - Republic of The Congo

FCRM will participate to the enrolment of a cohort of recovered COVID-19 individuals to assess long-term sequelae.

9.6. ZIKAction

Led by Penta, the ZIKAction research consortium brings together 14 partners across South and Central America, the Caribbean and Europe with the complementary goals of 1) developing a multidisciplinary multinational ready to-act network capable of rapidly addressing any maternal and paediatric research need arising from (re-)emerging infectious diseases including Zika virus and 2) conducting an interdisciplinary programme of research studies within this network to address key knowledge gaps relating to ZIKV epidemiology, natural history and pathogenesis, with a particular emphasis on maternal and child health. ZIKAction is funded by the European Union's Horizon 2020 Programme. ZIKAction works closely with two other European Union-funded consortia, ZikaPLAN and ZIKAlliance, to establish a Latin American and Caribbean network. Within this research consortium, the SARS-oV-2 sub-study will address issues related to COVID-19 infection in pregnant women and children.

9.6. Servicio Andaluz de Salud (SAS) - Hospital Universitario Virgen Macarena (HUVM)

SAS is a public body providing healthcare services to the 8.4 million inhabitants in Andalusia, Spain. Hospital Universitario Virgen Macarena (HUVM) belongs to SAS and is a reference 900-beds hospital located in Seville. The Department of Infectious Diseases, Microbiology and Preventive Medicine has a vast experience in different fields of infectious diseases; it includes

a multidisciplinary research group formed by basic scientists, clinical microbiologists, pharmacists and infectious diseases researchers performing basic and clinical research in this field. It hosts the coordination of the Andalusian Network for Clinical Research in Infectious Diseases (ANCRAID), the Spanish Network for Research in Infectious Diseases (REIPI) and is part of the Institute of Biomedicine of Seville (IBiS).

9.7. Universidade Federal de São Paulo (UNIFESP) - Escola Paulista de Medicina

A total of 1.652 patients diagnosed with COVID-19 confirmed by RT-PCR were hospitalized for at least 48 hours at Hospital São Paulo (HSP, UNIFESP), a 740-bed teaching hospital, located in the city of São Paulo, Brazil, between March 1st 2020 and April 30th 2021. Nearly 44.9% (N=723) of these patients were admitted to intensive care units and 1.152 were hospital discharged. UNIFESP will contribute with a retrospective and prospective cohort of COVID-19 patients admitted to HSP and followed-up every 3 months, providing demographic, epidemiological, clinical, imaging and laboratory data.

9.8. University of Bologna (UNIBO)

UNIBO has been involved in different research activities to tackle the diffusion of the virus. The Department of Medical and Surgical Sciences of UNIBO has been actively working, since the end of February 2020, to manage the COVID-19 pandemic both at clinical and research level in close collaboration with the Infectious Diseases Clinical Unit of the University Hospital S.Orsola-Malpighi and the Public Healthcare Provider governance of the Emilia-Romagna Region.

10. INCLUSION AND EXCLUSION CRITERIA

Inclusion criteria:

- Any age
- Any comorbidity
- Laboratory confirmed SARS-CoV-2 infection by PCR diagnosis from nasopharynx, oropharynx, bronchoalveolar lavage, stool, or blood. Rapid tests are an acceptable alternative.
- Person (or attorney or deputy who has been authorized to make the decision for patients who lack capacity) consent to participate.

Exclusion criteria:

• Refusal to participate to the study.

11. RECRUITMENT STRATEGY

Inpatients will be recruited by the study team at the treating hospital. Outpatients will be recruited by the study team in the emergency rooms, outpatient clinics, and through the coordination with regional primary care networks, who will offer the opportunity to enter the study to patients with active or previous COVID-19. This allows a broad recruitment of cases and the rapid inclusion of additional study centers in regional hotspots.

Patients will be followed up for up to 18 months after the SARS-CoV-2 infection diagnosis. The recruitment can take place at any time between the SARS-CoV-2 infection diagnosis and the end of the 18month follow-up, provided that the patient ensures at least one follow-up visit. Discharged inpatients as well as recovered outpatients will be invited to participate by a phone call (which will be repeated once in case of no reply). The screening/baseline data collection (including the informed consent process) can be carried out on the same day of a follow-up visit.

Before the first patient is recruited at a location, the responsible investigator ensures that all legal and regulatory requirements are met. Patients can revoke their consent to participate in the study without restriction at any time and at their own request, without giving reasons and without any consequences for their future treatment. In case of loss to follow-up, the previous follow-up assessments will be included in the data analyses. Patients will be recruited until January 2023 and followed-up until June 2023, allowing a partial follow-up for participants whose SARS-COV-2 infection occurred after January 2022.

12. STUDY PROCEDURES

The assessments of this study are designed to improve the COVID-19 patient care in the context of routine clinical care. Considering the lack of standardized follow-up pathways for COVID-19 patients, the selection of assessments has been based on available evidence and according to the definition of good clinical practice.

The organization of follow-up visits will be up to each center, according to the facilities and logistics of outpatient monitoring.

There will be a modular data capture according to the level of commitment of each cohort.

- Level I: Assessments in level I are mandatory
- Level II: Customized according to the feasibility of each cohort

The modular schedule of assessments is presented in Table 1. Overall, the follow-up will last 18 months. Day 0 corresponds to the time of the first positive SARS-CoV-2 test. The screening/baseline data collection (including the informed consent process, as detailed in section 14.3) can be carried out on the same day of a follow-up visit (as detailed in section 11). Procedures conducted as part of the participant's routine clinical management at the time of SARS-CoV-2 active infection and obtained before the signature of the informed consent form may be recorded, provided that the procedures meet the protocol-specified criteria.

Subsequent follow-up visits will occur at the following time-points: 3, 6, 2, 18 month(s). During each time-point, epidemiological data collection (SARS-CoV-2 vaccination status), treatment data collection (comorbidity management), clinical assessments (relevant medical new events, COVID-19 symptom assessment, physical examination, vital signs, 6-minute walking test), and the administration of questionnaires on functional status, respiratory impairment, and mental health will be performed as part of level I (mandatory) assessments, as well as the assessment of the SARS-CoV-2 immunological status (SARS-CoV-2 antibodies). A SARS-CoV-2 molecular test will be repeated only if it turned out positive at the previous follow-up visit.

Self-administered questionnaires on symptoms, as listed in Table 1, will be completed daily by the participant to provide timely data on the symptom length. The participant will assign a score based on symptom severity, which will be recorded daily in the self-administered diary: absent (0), mild (1), moderate (2) and severe (3).

As detailed in Table 1, level II (imaging, biochemistry, pulmonary function tests, electrocardiography) will be performed according to the capability of each cohort and will be based on the clinical evaluation, according to the participant's healthcare status. Imaging and biochemistry tests will be reassessed only if outside the normal ranges at the previous follow-up visit or if clinically indicated. During the follow-up visit at month 12, cardiac and lung ultrasounds, blood and urine tests will be offered as part of the participant's care.

COVID-19 biological samples (including blood, naso-pharingeal swabs, urine, and stool) will be collected and stored in the biobank of each participating center (according to local ethic commission recommendations). The Azienda Ospedaliera Integrata Universitaria (AOUI) of Verona developed a COVID-19-VR registry for biobanking COVID-19 biological samples to allow further research and national/international collaborations. As per protocol approved by the hospital Institutional Review Board (IRB 2577CESC), biological samples of COVID-19 patients are stored in the LURM (Laborato-

rio Universitario di Ricerca Medica). Test to be performed in a centralised laboratory (genomic, transcriptomic, cytokine, viral analyses, PBMCs and genetic and epigenetic see Table 2) will be sent, following international regulation, to the University of Antwerp, INSERM, University of Bologna or HMGU. A dedicated protocol will be developed for expeditions procedures. Nasal swabs collected prospectively for diagnosis of SARS COVID-2 will be collected in the local laboratory and sent out to University of Antwerpen and INSERM. Stool simple for microbiological analysis will be sent out to University of Bologna (see Table 2). Whole blood samples for epigenetic and genetic analysis will be sent out to UNIBO, INSERM and Helmholtz Zentrum Munchen (HMGU). In-depth human genetic analysis will be conducted using WGS or whole exome sequencing (WES) followed by functional analyses of the most promising variants. Genome-wide methylation analyses of COVID-19-positive patients in addition to a small number of control patients will enable differentiation of inherited and acquired genomic regulatory features through COVID-19 infection, which result in severe disease or an efficient clearing of infection through immune responses.

Table 2 - Samples collected at SARS-CoV-2 diagnosis and at follow up.

Sample	Aliquot	Sample type	Volume	Storage solu- tion	Storage temp. (°C)	Shipping temp. (°C)	Task	Comment	Partner
PBMC	1 or 2 samples	РВМС		0.5 ml FBS/DMSO 20%	-70°C or be- low or liquid nitrogen	Dry ice	Characterisa- tion of T-cell immune re- sponse		UANT- WERPEN
Blood	1	EDTA plasma, but heparin plasma or se- rum can also be used, if EDTA plasma is ab- solutely una- vailable	350 μL	EDTA plasma has to be pro- cessed accord- ing to the proto- col provided be- fore freezing (preferably at -80°C directly)	Short term at -20 °C, long term at -70°C or be- low	Dry ice	Cytokinome analysis	Please pro- cess and freeze within 2 hours.	UANT- WERPEN

	2	Se- rum/plasma	200 µL	NA	-20°C, long term at - 70°C or be- low	Dry ice	Auto-anti- bodies against type I IFNs	If available	INSERM
	3	Serum	100 µL	NA	-20°C, long term at -70 ° or below	Dry ice	Antibodies detection		INSERM; UANT- WERPEN
Whole blood	1	Extracted DNA or whole blood	4 μg if DNA, 2 ml if whole blood	NA	-20°C/ - 80°C	Dry ice	NGS of COVID-19 cohorts	DNA could be ex- tracted lo- cally or at HMGU.	INSERM/UN- IBO
	2	DNA or whole blood	750 ng in 45 μL if extracted DNA; otherwise 1 aliquot	TE buffer or wa- ter if extracted DNA	-20°C	Dry ice	Illumina EPIC DNA methylation	DNA could be ex- tracted lo- cally or at HMGU.	HMGU
NP swab	1	NP swab	400 μL	TRIzol; RNA later; DNA/RNA shield	-70°C or be- low	Dry ice	Characterisa- tion of viral markers Respiratory microbiome dynamics		UANT- WERPEN- INSERM
Stool sample or rec- tal swab	1	Stool (faecal swab if stool is unavaila- ble)	1-2 g	RNA later if possible, other- wise frozen.	+4°C (up to 24 h) long term at -70°C or be- low	Dry ice	Intestinal microbiome profiling		UNIBO

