3.2 Schedule of assessments (SoA)

Table 1 - Schedule of follow-up Assessments

	COVID-19 (2 weeks ¹ ± 2 weeks)	3 months ¹ ± 1 month	6 months ¹ ± 1 month	12 months ¹ ± 1 month	18 months ¹ ± 2 months
Screening/baseline					
Inclusion criteria ¹					
Demographics ²					
Healthcare setting ³					
Length of hospital stay, days					
ICU admission					
Medical history ⁴					
Treatment					
Comorbidity management ⁵	Х	Х	Х	Х	Х
Anti-COVID therapy ⁶	Х				
Antibiotic therapy ⁷					

Oxygen therapy ⁸	v	X*	X*	X*	X*				
SARS-CoV-2 vaccination ⁹	X X	X	X	X	X				
Clinical assessment	Λ	Λ	Λ	Λ	Λ				
Relevant medical new events ¹⁰	Х	Х	X	Х	Х				
COVID-19 symptom ¹¹ onset	X	Λ	Λ	Λ	Λ				
		V*	V*	V*	V*				
COVID-19 symptom end	X	X*	X*	X*	X*				
COVID severity ¹²	X X								
SOFA score		37	37	37	37				
Vital signs ¹³	X	X	X	X	X				
Physical examination ¹⁴	Х	X	X	X	X				
12-lead electrocardiography	X	X	X	X	X				
6-minute walking test	Х	Х	Х	Х	Х				
DLCO (diffusing capacity for car- bon monoxide)	Х	Х	Х	Х	Х				
Pulmonary function test ¹⁵	Х	Х	X	Х	X				
Questionnaires									
Functional status ¹⁶	Х	Х	Х	Х	Х				
Respiratory impairment ¹⁷	Х	Х	X	Х	Х				
Mental health ¹⁸	Х	Х	X	X	Х				
Perceived risk of re-infection/ad-									
mission/re-admission ¹⁹	Х	Х	Х	Х	Х				
Adherence to main preventative	Х	Х	Х	Х	Х				
non-pharmacological measures ²⁰	Λ	А	А	А	Λ				
SARS-CoV-2 vaccination: ac-									
ceptance/non-acceptance and rea-	Х	Х	Х	Х	Х				
sons ²¹									
Imaging									
Lung ultrasound	Х	X	X*	Х	X*				
X-ray	Х	Х	X*	X*	X*				
High-resolution CT scan	Х	Х	X*	X*	X*				
Cardiac ultrasound	Х	Х	X*	Х	X*				
Cardiac MRI ²²	X^{21}	X^{21}	X*	X^{21}	X*				
Biochemistry									
Blood tests ²³	Х	X	X*	Х	X*				
Arterial blood gas test	Х	х	X*	X*	X*				
(pO ₂ /pCO ₂ /pH)									
Urine tests ²⁴	Х	X	X*	Х	X*				
Immunology			1						
Immune - serology and type I IFNs autoantibodies	Х	Х	X	Х	Х				
Immune - cytokine and chemokine	Х	X ³⁵	X 35	X ³⁵	X *				
Immune - cellular	X	X 35	X 35	X 35	X *				
Microbiological tests-NP swabs	11								
Viral variant and metagenomics									
sequencing	Х	X*,34	X*,34	X*,34	X*				
EDTA whole blood									
Genetic and epigenetic analysis	Х	X	X	Х	Х				
Stool Sample (faeces or rectal									
swab)									
Metagenomic sequencing	Х		Х		Х				
	unctive variable	s for specific fr		ns					
HIV									
HIV-infection status ²⁵	Х	Х	X	X	Х				
HIV-Infection therapy 26	X	X	X	X	X				
Assessment of adherence to fol-	4 8								
low-up visits and antiretroviral	Х	Х	X	Х	Х				
therapy	-		_	-	-				

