8. OBJECTIVES

Main objectives of the study are:

- To describe characteristics of COVID-19 sequelae, including type, rate, and length through clinical, laboratory, and radiological assessments
- To investigate valuable, confounder-adjusted, associations between COVID-19 sequelae and COVID-19 severity, comorbidities, aetiology (SARS-CoV-2 variants), COVID treatment (including monoclonal antibodies), and trends in SARS-CoV-2 antibodies
- To describe the rate, the aetiology (SARS-CoV-2 variants), severity, and clinical determinants of COVID-19 re-infections

Furthermore, data retrieved from COVID-19 cohorts will address the following objectives:

- To compare the time course of the immunological response of the population with sequelae with the immunological response of the population without sequelae.
- To investigate immunological patterns related to specific long-term sequelae.

- To investigate possible associations of SARS-CoV-2 variants with COVID-19 severity, time course of the immunological response, and long-term sequelae.
- To describe the rate and severity of sequelae and immunological trends of COVID-19 in patients vaccinated against SARS-CoV-2.
- To describe the time course of intestinal and pulmonary microbiome after SARS-CoV-2 infection.
- To investigate possible associations of long-term sequelae with hypercoagulability
- To describe the relationship between risk perception of reinfection and the adherence to preventative measures over time after the SARS-CoV-2 infection, including vaccine acceptance.
- To describe the use of health care services among patients recovered from SARS-CoV-2.
- To identify human and viral genetic markers indicative of disease severity using WGS or WES followed by functional analysis of the most promising variants.

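### The daily diary named for symptom length cannot cover symptom time before enrolment, which may be as late as month 18, and the source of symptom dates is not recorded

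*Combined protocol and SAP*

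**What the plan says.** The first main objective in section 8 is "To describe characteristics of COVID-19 sequelae, including type, rate, and length through clinical, laboratory, and radiological assessments". Section 12 gives the instrument for symptom length: "Self-administered questionnaires on symptoms, as listed in Table 1, will be completed daily by the participant to provide timely data on the symptom length". Each symptom is scored daily from 0 to 3. No start day, stop day or subgroup is given for the diary, and it has no row in Table 1. The reference to Table 1 can only mean the symptom list in footnote 11.

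Section 12 sets the time origin: "Day 0 corresponds to the time of the first positive SARS-CoV-2 test". Section 11 sets the entry rule: "The recruitment can take place at any time between the SARS-CoV-2 infection diagnosis and the end of the 18month follow-up", on condition of at least one follow-up visit. It also provides for recovered outpatients to be invited by phone and for baseline to fall on the day of a follow-up visit.

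For visits, section 12 lists "COVID-19 symptom assessment" among the level I (mandatory) items at each time-point. In Table 1 the row "COVID-19 symptom end" has a plain mark at the acute visit and an asterisk at months 3, 6, 12 and 18. The asterisk footnote limits reassessment to cases with an abnormal previous result or a clinical indication.

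**The concern.** A daily diary runs forward from enrolment only. A patient who enters in the acute phase can have symptom length measured to the day. A patient who enters at month 12 can have a diary from then on, but everything earlier must be reconstructed. Two kinds of measurement would then be pooled under one name.

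The mix is unlikely to be random. COVID-HOME (section 9.4) follows non-hospitalised patients early and prospectively. The Congolese cohort (9.5) enrols people who have recovered. The São Paulo cohort (9.7) is partly retrospective and made up of inpatients. Source of date may therefore run alongside severity and calendar period, and through calendar period alongside variant and treatment. These are exposures in the second main objective. A source that was not recorded at the time cannot be restored at analysis.

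The visit schedule is the natural back-up, so it matters whether symptoms are asked about at every visit or only when the last answer was abnormal.

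**Working it through.** The plan gives no figure on this point to reproduce. The 10,000 in section 13 is an expected enrolment and does not enter. The check is arithmetic on the enrolment window and visit windows, then a comparison of text.

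**1. Diary coverage.** Inputs: 18 months of follow-up from day 0 and enrolment at month m (section 11). Maximum coverage = (18 − m)/18.

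- m = 3: 15/18 = 83%
- m = 6: 12/18 = 67%
- m = 12: 6/18 = 33%
- m = 18: 0/18 = 0%

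These are upper bounds. They assume that the diary is kept every day to month 18, and section 11 accepts partial follow-up for infections after January 2022.

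**2. Episodes finished before the diary could start.** Calendar coverage is not episode coverage, so a second calculation is needed. The documents give no resolution times. As an assumption, take exponential resolution from day 0 with median M months. Share already over at enrolment = 1 − 0.5^(m/M).

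| Enrolment | M = 1 | M = 3 | M = 6 |
|---|---|---|---|
| Month 3 | 88% | 50% | 29% |
| Month 6 | 98% | 75% | 50% |
| Month 12 | about 100% | 94% | 75% |

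Episodes in these shares would have no diary data at all. This illustrates what could happen; it does not estimate what will.

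**3. Resolution when dates rest on visits.** Widest gap between visits = (later visit + its window) − (earlier visit − its window), from Table 1, taking two weeks as 0.5 month.

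- Acute to month 3: (3 + 1) − (0.5 − 0.5) = 4 months
- Month 3 to 6: (6 + 1) − (3 − 1) = 5 months
- Month 6 to 12: (12 + 1) − (6 − 1) = 8 months
- Month 12 to 18: (18 + 2) − (12 − 1) = 9 months

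The diary resolves to one day.

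**4. Section 12 beside Table 1.** Section 12 requires a symptom assessment at every time-point. Table 1 makes symptom end conditional from month 3. If the condition governs the whole symptom enquiry, a patient who was clear at month 3 need not be asked at month 6, and a symptom that returned in between is missed unless a diary catches it. If it governs only the end date, the two places agree. The text does not say which is meant.

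**5. Analysis.** Section 13 defines no symptom length, sets no order of preference among sources, and has no rule for delayed entry or interval censoring. It says only that procedures for censoring and imputation are to be developed.

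**The case against.** The strongest reply has four parts.

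- **The diary is not named as the only source.** The objective refers to clinical, laboratory and radiological assessments. Section 12 allows routine procedures from the active infection to be recorded, section 14.4 allows retrospective collection, and section 14.7 counts hospital and general practitioner records as source documents. This stands in part. A reader might infer that late entrants' lengths rest on recall alone, but records can supply past dates and late entrants can keep a diary from enrolment onward. It does not remove the problem, because no passage says how past symptom dates are to be obtained or asks for their source.

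- **Table 1 and section 12 can be read together.** Status may be asked at every visit and an end date entered only when one is outstanding. This also stands. A reader might call the two places a flat contradiction; the documents do not support that. A reader might further infer that onset is scheduled only at the acute visit, but the marks in the onset row are not legible enough in the public text to rely on. What remains is an ambiguity that should be removed.

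- **The size is unknown.** This is correct. With no distribution of enrolment times, any bias figure only gives back the recall error that was assumed. The documents do not support saying that lengths cannot be compared at all.

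- **Asking for dates at visits does not equalise recall.** A month-12 entrant looks back 12 months at once, while an acute-phase entrant looks back over one visit interval. This stands, and it is a reason to keep the diary data rather than replace them with visit dates.

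**Conclusion.** The concern holds as a measurement problem. Followed as written, the diary is left-truncated for late entrants, their earlier symptom time comes from recall or records, and nothing marks which source produced a date. The mix of sources will vary with enrolment time and probably with cohort, so pooled lengths and comparisons between cohorts, variants or treatment periods may partly reflect the source.

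The only size that follows from the documents is the ceiling on diary coverage, which falls from 83% for entry at month 3 to 0% at month 18. The shares of finished episodes rest on assumed exponential resolution. The size and direction of any bias cannot be stated.

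The symptom-end row is a point to reconcile, not a proven conflict. The plan should be changed, because length belongs to a main objective and an unrecorded source cannot be recovered later. The study remains viable.

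**What to change.** 1. **Table 1.** State that the presence of each footnote 11 symptom is asked at every attended visit, whatever the previous answer, with onset, end or recurrence dates entered only for symptoms reported. This brings Table 1 into line with the mandatory assessment in section 12. Give the diary's start and stop in section 12.
2. **eCRF.** Record the source of each date (diary, recall at visit, medical record) and the enrolment date relative to day 0.
3. **Section 13.** Define symptom length. Count diary-based length from enrolment as delayed entry, so that a patient contributes diary time only from that day. Add a sensitivity analysis of length restricted to patients enrolled within the acute window, and one by source of date.

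The cost is a few date and source fields per reported symptom, one table correction and one more analysis. Limiting dates to reported symptoms matters: footnote 11 lists 30 symptoms, and three dates for each at five time-points would be 30 × 3 × 5 = 450 fields per patient, against the aim in section 14.5 of keeping the burden low.

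Differences in recall length between early and late entrants will remain after these changes and should be stated as a limitation.
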